8.4.6 Cardiovascular and Death Events

BAY 1834845 and its metabolite M-5 (BAY 2822815) did not show activity at potential offtargets and did not interact with cardiac ion channels (human ether-à-go-go-related gene [hERG], human sodium channel/current isoform 1.5 [hNav1.5], and human calcium channel/current isoform 1.2 [hCav1.2]).

In-vivo, BAY 1834845 was devoid of acute adverse effects on vital organ functions in rats (central nervous and respiratory system), and in both Beagle dogs and Cynomolgus monkeys (hemodynamic and electrocardiogram parameters).

In the FiM study (18384), no TEAEs were reported relating to changes in vital sign values nor to cardiac-related symptoms following treatment with zabedosertib.

In the drug interaction study (18387, Part B), one subject had documented palpitations; there were no subjects with clinically significant ECG findings, and no further TEAEs were reported relating to changes in ECG values following treatment with zabedosertib.

In the multiple dose study (18385), one subject had documented palpitations; there were no subjects with clinically significant ECG findings, and no further TEAEs were reported relating to changes in ECG values following treatment with zabedosertib. No new safety findings related to cardiovascular and death events were identified from Study 21329.

8.4.7 Disease-related Events and/or Disease-related Outcomes Not Qualifying as AEs or SAEs

Not applicable.

8.4.8 Adverse Events of Special Interest

Adverse events of special interest (AESIs) will include:

- Confirmed or suspected severe invasive bacterial infections
- Systemic hypersensitivity reactions
- Non-invasive infections (skin)
- Unexplained cases of rhabdomyolysis

AESIs must be reported in an expedited fashion as described for SAEs in Section 10.3.4.

8.5 Pharmacokinetics

8.5.1 PK measurements of zabedosertib and its metabolite M-5

Sparse blood samples for PK analyses of zabedosertib and its metabolite BAY 2822815 (M-5) in plasma will be collected at the time points given in the study SoA (Section 1.3). Details about the collection, processing, storage and shipment of samples for PK analyses will be provided separately (e.g., sample handling sheets or laboratory manual) and available at the Investigator Site File.

The PK analyses will be performed using validated analytical methods. Quality Control (QC) and calibration samples will be analyzed concurrently with study samples. The results of calibration samples and QC samples will be reported in the Bioanalytical Report, which will be included in the Clinical Study Report for this study. Concentrations are calculated from the chromatographic raw data in accordance with current Bayer guidelines.

The PK evaluation, if applicable, will be based on the actual sampling and dosing times.

Blood samples will be considered valid for the population PK analysis (see below) under the following conditions:

- 1. The dose amount and time of drug intake prior to the blood sample is known
- 2. The time of the blood sample collection is known

Therefore, it is important to have these data thoroughly documented in the CRF. Deviations from the specified time points are possible and should not be considered as protocol violations. Exact collection dates and times of the PK samples and the times of the evening and morning doses of the previous day as well as the time of the morning dose on the visit day must be documented. In addition, to reassure PK results drug measurements may be performed from samples taken for other laboratory investigations (e.g., safety lab). The results of those measurements will be reported internally in the PK study file.

No non-compartmental analysis assessment will be performed. Measured concentrations will be listed and presented by descriptive statistics.

Drug concentration information that would unblind the study will not be reported to investigative sites or blinded personnel. The bioanalyst will remain unblinded for analysis of study samples.

8.5.2 Population pharmacokinetic (popPK) evaluation

The variability in the pharmacokinetics of zabedosertib (and optionally its metabolite BAY 2822815), drug-related pharmacodynamic (PD) biomarker and/or safety and efficacy measurements collected during the trial might be analyzed using nonlinear mixed effects modeling.

Mixed effects models, e.g. population pharmacokinetic (popPK) models, describe the relationship between dose and time and variables such as drug plasma concentrations or clinical response. Both structural and random effects are involved in this relationship. A previously developed population PK model based on phase-1 data will be further developed to evaluate the variability in PK based on intrinsic factors (e.g., body weight, race) and extrinsic factors (e.g., concomitant medication) (covariates) that are of clinical relevance. If applicable, a separate Modeling and Simulation (M&S) analysis plan, providing details of the

model development and evaluation will be provided prior to the beginning of the population PK analysis and results will be presented in a separate M&S Report.

The population PK analysis might start prior to database lock. If this is applicable, appropriate measures will be taken to maintain blinding of the study team, e.g. data will be stored separately, and members of the study team will neither have access to the randomization list nor to individual data.

PK/PD and/or exposure-response evaluations might be conducted to evaluate the relationship between zabedosertib pharmacokinetics and or exposure and specific PD and/or safety and/or efficacy measures. If applicable, a separate M&S analysis plan, providing details of the methodology and evaluation will be provided prior to the beginning of the PK/PD and/or exposure-response analysis/ analyses and the results will be presented in a separate M&S Report(s).

The PK/PD and/or exposure-response evaluations might start prior to database lock. If this is applicable, appropriate measures will be taken to maintain blinding of the study team, e.g. data will be stored separately, and members of the study team will neither have access to the randomization list nor to individual data.

8.6 Pharmacodynamics

None.

8.7 Genetics

In this study, no genetic sampling will be performed.

8.8 Biomarkers

In this study, genetic as well as non-genetic biomarkers will be investigated.

Skin biopsy substudy (formalin fixation)	Skin sample 1	IHC (protein expression)
Skin biopsy substudy (RNA fixation)	Skin sample 2	mRNA expression
BM plasma	Blood sample 1	Inflammatory markers / other exploratory BMs
BM whole blood	Blood sample 2	e.g. Kinase activity

Table 8–1: Sample types for biomarkers

BM = biomarker; (m)RNA = (messenger) ribonucleic acid; IHC = immunohistochemistry

- Timing see SoA (Section 1.3) for planned time points of sample collection.
- Sample handling and storage details on the collection, processing, shipment and storage of samples will be provided in separate documents (e.g., lab manual). Samples may be stored for a maximum of 15 years (or according to local regulations) following the end of the study at a facility selected by the sponsor to enable further analyses.
- Medical history information if any additional information about the status of disease was collected in the course of treatment prior to entry of the participant in the study, the results may be collected in order to include this data in biomarker analyses.

• Reporting – the results of biomarker investigations may be reported separately (e.g, gene expression analysis of skin biopsies in a biomarker evaluation report).

An exploratory biomarker (BM) analysis will be conducted in this study. The sample types are summarized in Table 8–1.

Skin biopsy samples will be collected from a subgroup of participants willing to participate in this substudy, independent of the study intervention (n = approximately 40) at time points defined in the SoA. See Section 10.5.

8.8.1 Biomarkers Monitoring Disease Activity

AD is the most common, complex chronic inflammatory skin disease. PD biomarkers will be evaluated in samples collected before and during treatment in order to determine the impact of the study intervention on these biomarkers.

Candidate PD biomarkers may give hints to drug efficacy and may include (but are not limited to) for example:

- Skin biopsies: Molecular analysis (gene expression (customized host response panel [NanoString] with addtl. AD-specific probes); immunohistochemistry (eg K16, Ki 67), optional analysis) of the lesional skin biopsies will be performed. in a substudy (n = approximately 40 planned). See Section 10.5.
- Blood: Plasma levels of inflammatory markers and kinase activity (optional analysis).

In addition, a blood sample may be subjected to a further inflammatory BM analysis in order to identify biomarkers which respond to treatment or biomarkers which may indicate disease progression (optional analysis).

8.8.2 Other Biomarkers

BMs related to the mode of action or the safety of zabedosertib may be examined in addition to the BMs described above.

Further BMs deemed relevant to atopic dermatitis or other inflammatory diseases of the skin and associated health problems may be examined in addition to the BMs described above. Those investigations may include, e.g. diagnostic, safety, PD, monitoring, or potentially predictive BMs.

8.9 Immunogenicity Assessments

See Section 8.4.8.

8.10 Health Economics

Health economics parameters are not evaluated in this study.

8.11 Other Procedures

Photographs of a representative area of AD involvement (e.g., the lesioned area used for EASI assessments) may be taken on an individual basis at selected sites (optional procedure) to exemplary document the course of disease during the study. The photographs taken in this study are primarily planned to be used for publication purposes. The sponsor will check the quality of the received image data. Instructions for taking the photographs (for timepoints, see SoA in Section 1.3) will be provided and available in a specific manual.

9 Statistical Considerations

The analysis and reporting will be done on all data from all participants at the time the study ends.

The statistical analysis plan will be finalized prior to unblinding and it will include a more technical and detailed description of the statistical analyses described in this section. This section is a summary of the planned statistical analyses of the most important endpoints including primary and key secondary endpoints.

9.1 Statistical Hypothesis

The primary efficacy endpoint is achievement of 75% reduction from baseline in the EASI (EASI 75 response) at Week 12 (Day 84, EOT).

Let π_{BAY} and π_{Plac} be the responder rate with respect to EASI 75 after zabedosertib and placebo, respectively.

The statistical hypothesis of the study is defined as follows:

 $\pi_{\text{BAY}} > \pi_{\text{Plac}}$ ('clinical activity' criterion),

i.e. that the EASI 75 responder rate after treatment with zabedosertib is higher than after placebo.

The study will be evaluated using Bayesian statistics, which allows to determine the posterior probability in favor of a hypothesis. Therefore it is not needed to specify a pair of hypotheses. The statistical hypothesis will be considered accepted if the posterior probability for the hypothesis of interest is higher than 90%.

9.2 Analysis Sets

The analysis sets are defined in Table 9–1.

Table 9–1: Analysis sets

Analysis set	Description
Enrolled	All participants who signed the ICF.
All Randomized (RAND)	All participants randomly assigned to study intervention Participants will be analyzed according to the intervention they were randomized to.
Safety analysis set (SAF)	All participants who took at least 1 dose of study intervention.
	Participants will be analyzed according to the intervention they actually received.
Per protocol set (PPS)	 All randomized participants who meet the following criteria: have an EASI score at baseline have an EASI score at Day 56 (Visit 6) or later or took rescue medication between Day 56 (Visit 6) and Day 84 (Visit 7) or took SoC or discontinued study intervention due to lack of efficacy (at any time) showed compliance of at least 80% with study intervention between start of treatment and end of treatment or start of rescue medication at or after Day 56 (Visit 6), whatever comes first showed compliance of at least 80% with study intervention during the last 4 weeks before end of treatment or start of rescue medication at or after Day 56 (Visit 6), whatever comes first. are without validity findings with respect to the efficacy related entry criteria Participants will be analyzed according to the treatment they actually received.
Pharmacokinetic set (PKS)	All participants who – were treated with zabedosertib, – have at least 1 valid zabedosertib plasma concentration sample, – are without protocol deviations, which would interfere with the evaluation of the PK data. See Section 8.5.1 for PK details

Details on additional analysis sets which may be of interest will be provided in the SAP.

The assignment of participants to the analysis sets will be decided before unblinding.

9.3 Statistical Analyses

The SAP will be finalized prior to unblinding (the final SAP is prerequisite for Blind Review Meeting), and it will include a more technical and detailed description of the statistical analyses described in this section. This section is a summary of the planned statistical analyses of the most important endpoints including primary and specific secondary endpoints. If not otherwise indicated, the statistical analyses will be performed using the Statistical Analysis System (SAS); the version used will be specified in the SAP.

9.3.1 General Considerations

Continuous variables assumed to be normally distributed will be summarized using number of participants, mean, standard deviation, minimum, median, and maximum. Continuous variables assumed to be log-normally distributed will be summarized using number of participants, geometric mean, geometric standard deviation, geometric coefficient of variation, arithmetic mean, arithmetic standard deviation, arithmetic coefficient of variation, minimum, median, and maximum.

For categorical data frequency tables will be provided.

In general, summary statistics and frequency tables will be presented by treatment group, visit and time point (if applicable). Plots over time (if applicable) will also be presented by treatment group.

9.3.2 Efficacy Analyses

The primary efficacy analysis will be performed on the PPS.

9.3.2.1 Primary Efficacy Endpoint

The primary efficacy endpoint is achievement of 75% reduction from baseline in the Eczema Area and Severity Index (EASI 75 response) at Week 12 (Day 84). The EASI score ranges from 0 to 72. The lower the EASI score the better the state of the participant with respect to severity and extent of AD symptoms.

The analysis of the primary efficacy endpoint on the PPS will be performed as follows:

The impact of a potential use of rescue medication (TCSs or TCIs) or SoC for treatment of AD on the efficacy effect will be accounted for as follows:

If rescue medication is used between Day 56 (Visit 6) and Day 84 (Visit 7) or if SoC is used (at any time), the participant will be specified as a non-responder with respect to the EASI 75 response from the time the rescue medication or SoC medication is used.

If a participant discontinues study intervention due to lack of efficacy at any time (e.g., due to an adverse event related to AD such as disease flare), the participant will also be specified as a non-responder with respect to EASI 75 response from the time of the discontinuation.

Otherwise, missing data - e.g. due to study intervention discontinuation due to other reasons such as reasons related to Covid-19 pandemic (individual reasons or prevention/logistic measures), withdrawal of consent not due to lack of efficacy or adverse events not related to AD - will be imputed using a multiple imputation approach based on logistic regression model. Details will be specified in the SAP. Furthermore, alternative imputation methods might also be specified in SAP.

The following supplementary analyses will be performed to further assess rescue medication use. The study participant is considered a non-responder in case of rescue medication use between the EOT visit and

- baseline
- 1 week after baseline,
- 2 weeks after baseline,
- 4 weeks after baseline,
- 6 weeks after baseline.

One additional analysis will be performed where rescue medication does not trigger the classification as non-responder at all to assess the effect of combined treatment of zabedosertib with topical AD medication.

Participants who take SoC medication or who discontinue study intervention due to lack of efficacy will still be counted as a non-responder for the time points after SoC use or discontinuation of study intervention due to lack of efficacy as described above.

Bayesian inference will be used to quantify the EASI 75 responder rates on Day 84 in the zabedosertib and placebo treatment group. For each treatment group a non-informative Beta(1,1) prior will be used. The Beta(1,1) prior produces a posterior distribution in the same distribution family, namely Beta(k+1,n-k+1) with k being the number of EASI 75 responders in the respective treatment group and n being the number of all participants in the respective treatment group. Simulations based on the posterior distributions of the EASI 75 response rate in both treatment groups will then be used to calculate the posterior probability P($\pi_{BAY} > \pi_{Plac}$ | data). In addition, median and 90% and 95% credible intervals will be calculated based on the posterior distributions for the response rates in both treatment groups as well as for the difference between both treatment groups.

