•	Missing baseline value EASI assessment: exclusion from analysis as adequate imputation of response information is considered not possible
•	Missing Day 84 (Visit 7) EASI assessment:
	imputation of response information using data from Day 56 (Visit 6) or later (hypothetical strategy), if none of the conditions applies which are described above.
•	Missing Day 56 (Visit 6) and later EASI assessment: exclusion from analysis unless participant is a non-responder due to use of rescue medication, SOC or treatment discontinuation due to lack of efficacy

4 Study Design

4.1 **Overall Design**

Study 22158 is a Phase 2a proof of concept (PoC) study.

Randomized, placebo-controlled, double-blind, 2-arm, parallel-group, multi-center Phase 2a study. The study consists of

- a 28-day screening period (Visits 1 and 2),
- a 12-week intervention period consisting of 5 visits (Visits 3, 4, 5, 6, and 7),
- and a 4-week follow-up (FU) period with one visit (Visit 8).

Thus, the total study duration per participant will be 17 to 20 weeks (approximately 140 days), with 8 study visits at intervals of 8 to 28 ± 3 days.

Screening period

During the screening period, potential study participants will be identified, and informed consent will be obtained prior to the initiation of any study-related procedures. Participants will then be evaluated for eligibility against the study-specific inclusion and exclusion criteria.

Emollients used by the participant before entering the study should be continued with the same frequency/intensity. At least 7 days before the randomization visit, participants are required to use a stable amount (i.e., approximately the same amount for each application) of topical drug-free emollient to moisturize the skin applied to the whole body twice a day, which should continue during the study.

During the same 7-day period, participants will daily record the intensity of their peak pruritus using a 0-10 numerical rating scale (NRS) [Peak Pruritus 0-10 NRS] displayed on the electronic patient handheld device.

Randomization

Randomization will be done at the randomization visit on Day 1, i.e. at the end of the screening period.

A total of 72 participants are planned to be randomly allocated to 1 of the 2 treatment groups with a 2:1 allocation ratio to achieve a total of 57 participants valid for efficacy analysis:

zabedosertib at a dose of 120 mg BID:	48 randomized / 38 valid for the efficacy analysis

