9.5 Sample Size Determination

A Bayesian concept will be used for inference, which is based on the posterior probability that the research hypothesis is true. Therefore, it is the goal of this study to demonstrate that zabedosertib is superior to placebo with posterior probability > 90%, i.e. $P(\pi_{BAY} > \pi_{Plac} | data) > 90\%$ (='clinical activity' criterion).

The EASI 75 responder rate of 0.49 for assumed systemic standard of care (SoC) dupilumab was derived as the mean responder rate from a meta-analysis on the active treatment arms in two Phase 3 AD studies (Simpson et al, 2017), comprising 919 participants.

Non-informative Beta(1,1) priors will be used for the Bayesian inference. For Placebo, a response rate of 16% was assumed. The statistical power was determined with SAS 9.4. Assuming that the EASI 75 responder rate in zabedosertib-treated participants is 0.49, evaluable data from 57 participants (38 on zabedosertib, 19 on placebo) will provide at least 90% power to establish superiority of zabedosertib. Approximately 72 participants will be randomly assigned to the study to obtain 57 evaluable participants overall (2:1 randomization zabedosertib versus placebo).

10 Supporting documentation and operational considerations

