4.2.4 Supplementary Analyses

Handling of use of rescue medication

The following supplementary analyses will be performed on the PPS to further assess the influence of rescue medication use on the EASI 75 response.

The analysis will be performed with a different handling of the following intercurrent event:

• Use of topical rescue medication: At Day 56 (Visit 6) or later (until Day 84 (Visit 7) or end of treatment if before Day 84 (Visit 7)): analyze study participant as non-responder (composite strategy)

Before Day 56 (Visit 6): disregard use of topical rescue medication (treatment policy strategy)

Use of rescue medication will be handled for supplementary analyses as outlined in the following:

The study participant is considered a non-responder in case of rescue medication use between the EOT visit and

- Baseline,
- 2 weeks after baseline,
- 4 weeks after baseline.

One additional analysis will be performed where rescue medication does not trigger the classification as non-responder at all to assess the effect of combined treatment of zabedosertib with topical AD medication.

If rescue medication does not trigger the classification as non-responder, the EASI 75 response will be based on the EASI scores collected after use of rescue medication.

Participants who take SoC medication or who discontinue study intervention due to lack of efficacy will still be counted as a non-responder for the time points after SoC use or discontinuation of study intervention due to lack of efficacy as described above.

The EASI score at time points after discontinuation of treatment due to other reasons not related to lack of efficacy or otherwise missing values will be imputed using "worst case" and last observation carried forward as described in Section 4.2.3. No multiple imputation approach using logistic regression will be performed for the supplementary analysis due to potential scarceness of participants continuing until Day 56 (Visit 6) without any rescue medication.

All other intercurrent events will be handled as described for the primary estimand.

Analysis on FAS

The EASI 75 response will be analyzed on the FAS according to the supplementary estimand (refer to Section 1.1). Imputation techniques in case of missing EASI 75 response information at Day 84 (Visit 7) will be as for the primary analysis.

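### In the PPS rescue-timing analyses (B_2.1 to B_4.2), some participants rescued before Day 56 are non-responders by rule but fall outside the analysis set

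*Protocol*

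**What the plan says.** Protocol 9.3.2.1 announces supplementary analyses with earlier rescue cut-offs: "The study participant is considered a non-responder in case of rescue medication use between the EOT visit and" a list of time points that starts at baseline. SAP 4.2.4 keeps baseline, 2 weeks and 4 weeks, numbers them B_2.1 to B_4.2 in Table 4-1, and names the analysis set: "The following supplementary analyses will be performed on the PPS to further assess the influence of rescue medication use on the EASI 75 response".

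The PPS (Protocol 9.2, Table 9-1; SAP Section 3) requires a baseline EASI and one of four further conditions:

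1. an EASI at Day 56 or later;
2. rescue in a fixed window, worded as "took rescue medication between Day 56 (Visit 6) and Day 84 (Visit 7");
3. use of SoC;
4. discontinuation for lack of efficacy at any time.

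Compliance and entry-criteria conditions apply as well.

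Two rows of the primary estimand (Protocol 3.2; SAP 1.1) bear on early leavers. One excludes anyone who stops before Day 56 for a reason unrelated to efficacy, on the ground that response cannot be adequately imputed. The other, on missing EASI from Day 56 onward, prescribes "exclusion from analysis unless participant is a non-responder due to use of rescue medication, SOC or treatment discontinuation due to lack of efficacy".

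On the FAS, SAP 4.2.4 repeats only the rule that counts rescue from Day 1 (B_7.1, B_7.2). The 2-week and 4-week rules have no FAS version.

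**The concern.** The rescue rule moves with the analysis, but the rescue route into the analysis set does not. Elsewhere the SAP does move it: Sections 8.3 and 8.4.1 repeatedly attach a Day x alternative for the supplementary analyses to the Day 56 rule. The set definition has no such alternative.

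The reason given for excluding early leavers is that their response cannot be imputed. Under the earlier cut-offs that reason does not apply to someone already rescued, because the rescue itself fixes the outcome as non-response. B_2 to B_4 also use no multiple imputation, so they do not need the Day 56 EASI on which the primary imputation model depends.

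These analyses exist to show how far the result depends on disregarding rescue before Day 56. Excluding some of the early-rescued removes failures from the check designed to count them. Each arm's response rate is then overstated, by more in the arm that loses proportionately more such participants.

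**Working it through.** **1. The plan's own figure.** Inputs are from Protocol 9.1 and 9.5. The criterion is "The statistical hypothesis will be considered accepted if the posterior probability for the hypothesis of interest is higher than 90" per cent. For the prior, "Non-informative Beta(1,1) priors will be used for the Bayesian inference". For the rates, "For Placebo, a response rate of 16% was assumed", with 0.49 for zabedosertib. The claim is that "evaluable data from 57 participants (38 on zabedosertib, 19 on placebo) will provide at least 90% power to establish superiority of zabedosertib".

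With k responders of n, each arm's posterior is Beta(k+1, n−k+1), and

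P = ∫ f(x; k_T+1, n_T−k_T+1) · F(x; k_C+1, n_C−k_C+1) dx,

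where T is zabedosertib, C is placebo, f is the Beta density and F the Beta distribution function. Summing Bin(k_T; 38, 0.49) · Bin(k_C; 19, 0.16) over all outcomes with P > 0.90 gives power 0.910. The stated figure reproduces. It belongs to the primary analysis and does not depend on this point.

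**2. Tracing one participant.** Suppose rescue on Day 20, a stop on Day 45 for a reason unrelated to AD, no SoC and no later EASI, with the compliance and entry conditions met.

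| Question | Answer |
|---|---|
| Non-responder in B_2 (rescue after Day 1)? | Yes |
| Non-responder in B_3 (rescue at/after Day 14)? | Yes |
| Non-responder in B_4 (rescue at/after Day 28)? | No; it would be yes for rescue on, say, Day 35 |
| PPS route 1, EASI at Day 56 or later? | No |
| PPS route 2, rescue on Day 56 to 84? | No |
| PPS routes 3 and 4, SoC or lack of efficacy? | No |
| In the PPS? | No |
| In the FAS (B_7)? | Yes, if a valid EASI exists from Day 14 on |

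The outcome is defined in B_2 and B_3, yet the participant is absent from both. The two estimand rows also disagree: one excludes this participant as an other-reason stop before Day 56; the other exempts a non-responder due to rescue.

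**3. Size.** The documents give no count of such participants, so the counts below are assumptions. The plan randomizes 48 and 24 for 38 and 19 evaluable. That leaves 48 − 38 = 10 and 24 − 19 = 5 planned non-evaluable for all reasons together, which serve as the outer limit. Adding a zabedosertib and b placebo non-responders leaves k unchanged and raises n to 38+a and 19+b.

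| Start | Added (a, b) | After | Difference in rates, before → after | P, before → after |
|---|---|---|---|---|
| 19/38 vs 3/19 | 2, 1 | 19/40 vs 3/20 | 0.342 → 0.325 | 0.994 → 0.993 |
| 19/38 vs 3/19 | 10, 5 | 19/48 vs 3/24 | 0.342 → 0.271 | 0.994 → 0.991 |
| 19/38 vs 3/19 | 10, 0 | 19/48 vs 3/19 | 0.342 → 0.238 | 0.994 → 0.966 |
| 19/38 vs 3/19 | 0, 5 | 19/38 vs 3/24 | 0.342 → 0.375 | 0.994 → 0.999 |
| 12/38 vs 3/19 | 1, 2 | 12/39 vs 3/21 | 0.158 → 0.165 | 0.885 → 0.909 |
| 12/38 vs 3/19 | 2, 1 | 12/40 vs 3/20 | 0.158 → 0.150 | 0.885 → 0.882 |
| 13/38 vs 3/19 | 2, 0 | 13/40 vs 3/19 | 0.184 → 0.167 | 0.918 → 0.899 |
| 15/38 vs 4/19 | 1, 2 | 15/39 vs 4/21 | 0.184 → 0.194 | 0.909 → 0.932 |

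The 19/38 vs 3/19 rows sit near the planning rates (0.49 × 38 = 18.6; 0.16 × 19 = 3.0). There the posterior stays above 0.96 even at the outer limit. Crossing 0.90 takes a result near the line together with loss that departs from the 2:1 allocation, and it can happen in either direction.

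**The case against.** The strongest reply is that a fixed set is deliberate. SAP 4.2.4 changes the handling of one intercurrent event and leaves the others as in the primary estimand, which excludes other-reason stops before Day 56. A participant absent from the primary analysis had no rescue disregarded there, and keeping the same people in B_1 to B_5 isolates the effect of the rescue rule. This has weight: it is why the fixed-PPS result should stay beside any revised one. It does not settle the matter, because the primary estimand also holds the exemption for non-responders due to rescue, and under the earlier cut-offs the two rows conflict.

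The gap is also narrow, for reasons that stand:

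- A reader might infer that the PPS admits rescue users without a Day 56 EASI only through rescue on Day 56 to 84. It does not: SoC use and lack-of-efficacy stops also qualify, and SAP 8.3 counts worsening-AD adverse events and a physician's switch to other therapy as lack of efficacy.
- Leaving before Day 56 need not mean having no Visit 6 score. Under SAP 8.4.1 an unscheduled or end-of-treatment EASI from Day 49 can be assigned to Visit 6, the latter if taken within three days of the last dose.
- Rescue does not itself end treatment or visits (Protocol 6.9.2).
- B_7.1 and B_7.2 count rescue from Day 1 on the FAS, which needs an EASI only from Day 14. A reader might infer that early-rescued leavers are never counted; for the baseline cut-off most of them are.

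The detailed binary imputation section (SAP 8.4.2) is redacted in the public copy, so any further handling there cannot be checked.

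**Conclusion.** The point holds in a limited form. In B_2.1 to B_4.2, a participant rescued at or after the analysis's cut-off but before Day 56 is excluded despite a defined outcome if three things hold: the participant leaves before Day 56, the reason is neither lack of efficacy nor SoC, and no EASI can be assigned to Day 56 or later. The gap is mainly in the Week 2 and Week 4 analyses.

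A reader might go further and infer that the primary result is biased, or that the exclusion favours zabedosertib. The documents support neither. The primary analysis disregards rescue before Day 56 by design and is untouched. The direction in the supplementary analyses depends on which arm loses more such participants, and the number may be zero. Nor do the documents attach a pass/fail rule to these supplementary analyses; the SAP calls the study exploratory, so a crossing of 0.90 affects interpretation only.

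The sizes above rest on assumed counts and assumed results. This is a worthwhile clarification at low cost, not a defect in the main inference.

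**What to change.** In SAP 4.2.4 and Table 4-1, state that for B_2.1 to B_4.2, rescue at or after that analysis's own cut-off satisfies the PPS rescue clause. Alternatively, add FAS versions of the Week 2 and Week 4 cut-offs.

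State which estimand row takes precedence in these analyses when a participant is both an other-reason stop before Day 56 and a non-responder due to rescue.

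Report each analysis's denominator by arm, next to the result on the fixed PPS, so that the effect of the rule and the effect of the set can be told apart.

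Leave the compliance period as defined. Ending it at an early rescue date might look like a natural companion change, but nothing here supports it. It would recalculate compliance over short periods and could remove participants as well as add them.

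The cost is one or two sentences and a derived flag per cut-off. The drawback is that denominators will differ slightly between the supplementary analyses. The wording must be settled before set assignment at the blind review.
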